2.3.7. Medication Storage and Accountability

The study investigators or the study coordinator will document the amount of study drug/placebo dispensed and/or administered to subjects, the amount returned by subjects, and the amount received from and returned to the UPMC-IDS. The study drug/placebo accountability records will be maintained throughout the course of the clinical trial.

2.3.7 Concomitant Medications

No changes are needed to the subject's usual medication while taking sodium NO₂/placebo. Subjects will hold their anti-coagulation regimen prior to the biopsies to reduce the risk of excessive bleeding. The concomitant medication list will be retrieved from the patient's medical record, confirmed with the patient on the phone and at Visit 1 and then assessed for changes at study contacts thereafter. Any patient status or medication change during the study period advised by subjects' health care team will be reviewed with the PI.

2.3.8 Rescue Medications

Not applicable

2.4 STUDY ENDPOINTS

Overall, study endpoints pre- and post-NO₂ will include:

1. Measures of physical function will include CPET indices:
 - a. gait speed,
 - b. strength (endurance, power),
 - c. balance as measured by non-invasive CPET (nCPET) aerobic capacity, SS fatigability assessment, 6 minute walk test, non-infrared spectroscopy assessments of blood flow, Short Physical Performance Battery (SPPB), handgrips, and accelerometryAnd,
 - d. pulmonary pressure and ventricular-pulmonary artery coupling, as measured by invasive CPET (iCPET)
2. Skeletal muscle bioenergetics: spectrophotometric, mitochondrial respiration, ribonucleic acid (RNA) isolation, protein isolation, electron microscopy
Serology: inflammatory peptides (interleukin (IL) 1, IL-6, IL-15, TNF α ; adipokines (leptin and adiponectin); vitamin D, glomerular filtration rate (GFR), brain natriuretic protein (BNP) or N-terminal pro b-type natriuretic peptide (NT-proBNP), thyroid stimulating hormone (TSH), glycosylated hemoglobin (HgbA1c) and platelet bioenergetics [using Seahorse

Extracellular Flux (XF) analysis]⁹, i.e., including glycolytic as well as basal and maximal respiratory rates.

3. Additional secondary factors include Quality of life (QoL) and related indices: questionnaires that include measures of sleep, depression, pain, cognitive function, physical activity, co-morbidities, frailty, nutrient intake, cardiac self-care efficacy, fatigability and HF, via the Kansas City Cardiomyopathy Questionnaire (KCCQ).

2.5 STATISTICAL ANALYSIS

2.5.1 Sample Size Determination

Formal sample size justifications based on statistical power for detecting significant differences at a strict 0.05 level are not applicable for a pilot study such as ours. We will use the descriptive statistics obtained herein for formal sample size and power computations in planning the larger subsequent trial to obtain more definitive findings. We will base our sample size on preliminary data from the present project, published statistical methods for sample size and power for approaches as similar as possible to the proposed analyses, and commercially available specialized software (PASS 2012[®]; Number Cruncher Statistical Systems, LLC, Kaysville, Utah) in planning the future trial to be proposed under the R01 mechanism.

2.5.2 Study Conduct Analysis

We will clearly document participant flow from the number contacted to numbers screened, randomized and completed using a CONSORT diagram, with numbers and reasons for any exclusions, withdrawals, missed assessments and terminations at each stage. We will describe adherence to NO₂ therapy as measured by queries to subjects, self-report of empty compartments on weekly phone calls and pill counts at the post visits using summary statistics as well as any post-randomization adjustments. Insights gleaned from study conduct analyses will be used to adjust protocol in the subsequent larger trial to increase its feasibility.

2.5.3 Efficacy Analysis

Overview-We will use SAS[®] version 9.3 (SAS Institute, Inc., Cary, North Carolina) for all analyses. The main focus of the analyses of the present pilot study will be to establish feasibility and obtain preliminary findings, and descriptive statistics needed for formal sample size and power computations for a subsequent larger randomized trial to be proposed under the R01 mechanism to obtain more definitive conclusions. Therefore, we will pay greater attention to magnitudes of effects rather than statistical significance alone, and similar to published pilot studies in other settings, also employ graphical methods such as needle plots that focus on change at the individual level rather than on average^{87, 88}. First, we evaluate the distributional characteristics of the data set, the prevalence of missing values and general data quality using appropriate descriptive statistics and graphical summarizations for all variables for each arm for each time point, as well as baseline to follow-up change scores. Second, the baseline measures and participant characteristics will be compared between the two arms using differences in magnitudes of the descriptive statistics, and independent samples *t*-, Wilcoxon rank sum, Kruskal-Wallis, chi-square or Fisher's exact tests, as appropriate. Any variables found to be meaningfully different will be noted when interpreting the findings. Third, main analyses below will be performed.

Aim 1-We will conduct Aim 1 analysis on an intention-to-treat basis. We will fit a series of linear mixed models using the SAS[®] MIXED procedure with baseline to follow-up change in primary outcome RPE, secondary outcome peak VO₂, and each of the other secondary outcomes as the

dependent variable; and treatment (NO₂/placebo), follow-up time (4 weeks) and their interaction as main factors of interest; baseline value of the dependent variable as the sole and a catch-all covariate; and a subject random effect to account for multiple follow-up measurements from each participant. We will construct appropriate means contrasts to compare the treatment groups at each of the follow-up time points. The magnitudes of the estimated means contrasts and graphical displays of individual change will be considered to support Aim 1 hypotheses rather than and in addition to statistical significance at the 0.05 level.

Aim 2-We will use Pearson and Spearman rank correlation coefficients between outcomes (e.g., fatigability, daily activity) and potential mediators (e.g., bioenergetics, pulmonary pressures), both cross-sectionally and in terms of change from baseline, both combined and within arm, to simply quantify the influence of potential mediators on outcomes. We are aware of the formal methods for mediation analyses to elicit contributory role of NO₂ and potential mechanism such as Baron and Kenny framework⁸⁹, reduction in treatment effect of NO after additionally adjusting for potential mediators, and mediation models using the SAS[®] %SOBEL and %INDIRECT macros⁹⁰⁻⁹². However, our small sample size in the present pilot study does not afford the opportunity to reliably employ such methods. We plan to perform a rigorous mediation analysis using the said methods in the larger follow-up trial being planned with the results of the present study.

Exploratory/Secondary/Sensitivity Analyses: We have proposed a main analysis treating RPE as a continuous variable for greatest statistical sensitivity in a small sample, but are aware that a clinically meaningful threshold may be 10 indicating fatigue^{33, 49}. Therefore, we will consider additional descriptive summarizations based on the said dichotomous operational definition. We will also consider stratifying by or adjusting for (as a covariate) the initial dose (20/40mg).

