We will ask participants to complete them interspersed among the physical function tests so as to reduce fatigue of both assessments.

The 3DFR issued at Visit 1 will be reviewed with the subject for clarification and completion as well as the ActiGraph diary.

Prior to departing, we will remind subjects to resume their usual medication regimen if changes were made with regard to diabetes.

If study team or subject feel as though any of the study procedures at this visit are not safe and/or would be too burdensome to the subject, subject may not complete all of the procedures at this visit.

Visit 3A

Subjects will be scheduled for an outpatient visit at the University of Pittsburgh Magnetic Resonance Research Center (MRRC) in UPMC Presbyterian 5±2 days from Visit 2. This is a non-fasting visit (patients will be asked to eat a light meal) and will last approximately 2-3 hours. Subjects who are identified to have the presence of metal or non-MRI compatible device will not complete Visit 3A (or 6A).

Subjects will undergo:

1. Collection of interval history, measurement of BP and other vital signs (temperature, pulse, RR, HR, SpO₂) by study or MRRC staff.
Any concern for medical instability after vitals and interval history are collected will prompt contact with a study physician, and possible physical exam before proceeding.
2. The study coordinator will clear the subject as safe for MRI prior to the enrollment. Then the safety protocol and procedures of the MRRC will be followed as well as a double check for safety. The MRS is an in-vivo test to measure maximal mitochondrial capacity to generate ATP. It will be performed on the subject's leg as they complete a flexion-extension exercise within the bore of the magnet as described below.

Prior to the exercise, the technician will collect a fully-relaxed (FRS), high resolution ³¹P spectrum of the resting muscle. Then the exercise protocol will be performed: Participants lay supine with the non-dominant knee (unless contraindicated) elevated at ~30° and straps are placed over the legs. Participants perform voluntary isometric contractions (kicking) repeatedly as hard and as fast as they can for two bouts each followed by a rest period. The protocol is designed to deplete PCr stores by 33-66% to ensure high signal to noise defining PCr recovery without inducing acidosis (pH <6.8), which inhibits oxidative phosphorylation.

82, 83

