3. Following completion of the MRS protocol, subjects will be provided parking and discharged.

Note: Visit 3B is an optional visit. Subjects who choose to do the right heart catheterization visits will need to have blood drawn for a basic metabolic panel, PT/INR, and CBC/diff/platelets, preceding Visit 3B by no longer than 30 days, per the UPMC Cath. Lab protocol. We will coordinate this draw at one of the study or if the subjects have bloodwork prescribed for their ongoing medical care. Subjects will be provided parking for the blood draw visit, if it requires a separate visit.

Visit 3B

This visit will be completed by the subjects in the recruited sample who have consented to invasive cardiopulmonary exercise testing (iCPET). Subjects may decline this portion of the testing at consent. This fasting visit will take place in the UPMC Presbyterian Cardiac Catheterization lab (Cath. Lab) within 5 ± 2 days from Visit 3A and last approximately 4-6 hours. Subjects with diabetes will receive advisement on issues related to blood sugar management per the standardized pre-catheterization protocol of the UPMC Cath. Lab. Subjects on warfarin or NOACs will be reminded by study staff to hold those medications 3 days prior and including the day of the catheterization.

Upon arrival in the Cath. Lab, subjects will undergo:

1. Collection of adverse events, interval history, measurement of BP and other vital signs (temperature, pulse, RR, HR, SpO₂), as well as completing a breathing test, called [spirometry](#), that assess subjects ability to breathe in and out. We will confirm appropriate medications were held per individual case.
2. Brief physical exam
3. Right heart catheterization

[name], Co-Investigator, or a qualified pulmonologist or cardiologist investigator will lead the UPMC protocol for right heart catheterization, with strict adherence for safety and sterile conditions as indicated, including the use of fluoroscopy to guide the catheter placement. PA (internal jugular approach) and radial artery catheters are placed. Systemic and PA pressures (PAP) are measured continuously during exercise provocation (described below). PCWP is measured at baseline and each minute thereafter. End-expiratory assessments of right atrial pressure (RAP), RV pressure, PAP, and PCWP are assessed.

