Hemodynamic effects of NO₂ in the HFpEF subjects included significant decreases in RA, RV systolic and diastolic, PA systolic/diastolic/mean, and PCWP. PCWP and MPAP decreased by 7.8 and 7.0 mm Hg, respectively (baseline median values 18 and 34 mm Hg, respectively). MetHb levels increased modestly but did not meet stopping criteria of the study. [name] presented his work at the American Thoracic Society Meeting in March, 2016. Overall, the data demonstrate feasibility and safety of aerosolized NO₂ in HFpEF, and in many respects corroborate the recently published analysis by Borlaug in a study of HFpEF patients aged 69 ±6 years that showed infused NO₂ benefits to acutely improve right heart hemodynamics during exercise¹. None of Borlaug's patients experienced hypotension or other adverse events. NO₂ levels were undetectable at baseline, but then increased to 8.39 ±1.88 μM. PCWP was substantially improved by NO₂ compared with placebo (p<0.0003). Likewise, cardiac output reserve improved with exercise (p<0.002) and an increase in cardiac output relative to O₂ consumption was normalized. NO₂ also improved pulmonary artery pressure flow relationships in HFpEF and increased left ventricular stroke work with exercise versus placebo, indicating an improvement in ventricular performance with stress.

As described in Section 1.4 Significance, the PI, [name], has an ongoing pilot study of oral NO₂ 40 mg tid with healthy controls, HFpEF and HFrEF subjects. Ten control subjects have completed the pilot without any significant product related adverse events. Mild and transient symptoms consistent with what other investigators have observed have been present in some of the other subjects.

Experience thus far in the pilot with heart failure subjects has suggested a tendency for a vasoactive response to nitrite not seen in the controls. Subjects with both HFrEF and HFpEF enrolled thus far have all required dose reductions to 20 mg tid to prevent hypotension. Thus we have adopted the stratified dosing as described for this protocol.

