2.3.4. Treatment Period

Subjects will undergo study treatment duration of 4 weeks plus up to approximately 3 weeks of sodium NO₂ or placebo three times daily. Three additional weeks are included to allow continuation of the study drug/placebo through the final outcome collection series of visits. This is considered appropriate to study benefits of oral NO₂ therapy to improve physical function in patients with HFpEF.

Randomization and Blinding

We will use the high quality pseudo-random deviate generator in SAS® (SAS Institute, Inc., Cary, North Carolina) to randomize participants to NO₂ or placebo in 1:1 ratio with a random block size. Block sizes will be revealed to the rest of the study team at the conclusion of the study to prevent educated guessing. Randomization will be stratified by the initial dose (20/40 mg) depending on whether age ≥80 or age 70-80 and hypotension risk to the extent possible within the small sample size. Study statistician will create schedules which pairwise link the randomization sequence number, participant identifier and treatment arm, and call in all prescriptions thereafter by the randomization sequence number. The independent research pharmacist at the institutional Investigational Drug Service will package all drugs/placebos to be similar in physical appearance. We have successfully employed the same process in other recently completed trials¹⁰⁵. Therefore, all participants and study personnel involved in assessments will be blind to treatment assignment.

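### The main Aim 1 models leave out the initial-dose stratum used in randomisation, so their confidence intervals may be somewhat too wide

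*Combined protocol and SAP*

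**What the plan says.** All references are to the combined protocol and SAP.

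- **Section 2.3.4, Randomization and Blinding:** "Randomization will be stratified by the initial dose (20/40 mg"), with initial dose set by age and hypotension risk. The commitment is qualified: "to the extent possible within the small sample size". Allocation is 1:1 with random block sizes that are not given.
- **Section 2.5.3, Aim 1:** linear mixed models for change in RPE (primary), peak VO₂ and each other secondary outcome. The terms are treatment, follow-up time, their interaction and a subject random effect, with the "baseline value of the dependent variable as the sole and a catch-all covariate". There is no stratum term.
- **Section 2.5.3, Exploratory/Secondary/Sensitivity Analyses:** "We will also consider stratifying by or adjusting for (as a covariate) the initial dose (20/40mg"). This is an intention to consider the analysis, and the choice between stratifying and adjusting is left open.
- **Section 2.5.1:** no power-based sample size. "We will use the descriptive statistics obtained herein for formal sample size and power computations in planning the larger subsequent trial".

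**The concern.** Stratified allocation balances the arms within each dose group, so differences between the groups largely drop out of the treatment contrast. If the model has no term for the group, those differences stay in its residual. The reported standard error then describes a less balanced design than the one that was run.

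At stake are the width of the CI, the level of the 0.05 test (which section 2.5.3 uses alongside effect magnitudes) and possibly the variance carried into planning the next trial. The choice of model is also left until after the data are seen. The size of the means contrasts, on which Aim 1 mainly relies, is not affected.

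**Working it through.** **Inputs from the documents.** N = 18, 9 per arm; 1:1 blocked allocation; one stratification factor with two levels; baseline as sole covariate; 0.05 level (two-sided assumed). There is no planned power, SD or effect size to reproduce.

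**Assumed, because the documents are silent.** Stratum effect d, in residual SD after baseline adjustment, equal in both arms: 0, 0.5 or 1. Smaller stratum: 2 to 9 of 18. Random blocks of 2/4 or 4/6. A lopsided split is plausible from the pilot experience in section 2.3.3 ("Subjects with both HFrEF and HFpEF enrolled thus far have all required dose reductions to 20 mg tid to prevent hypotension"), but the documents do not give one.

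**Model.** With one follow-up value per subject, the Aim 1 model reduces to ANCOVA. Baseline-only: 18 − 3 = 15 residual df, t = 2.131. With stratum: 18 − 4 = 14 df, t = 2.145.

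**Residual variance, closed form.** With p the share in one stratum, the expected baseline-only residual variance divided by the within-stratum variance is

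1 + d² × n p(1−p) × (16/17) / 15.

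For d = 1:
- 9/9: 1 + 4.5 × 0.941 / 15 = 1.28
- 12/6: 1 + 4.0 × 0.941 / 15 = 1.25
- 14/4: 1 + 3.11 × 0.941 / 15 = 1.20
- 15/3: 1 + 2.5 × 0.941 / 15 = 1.16
- 16/2: 1 + 1.78 × 0.941 / 15 = 1.11

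For d = 0.5 the excess is a quarter of this: 5-7% with 4-9 in the smaller stratum, 3-4% with 2-3.

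**CI width and test level, simulated.** 6,000 null trials per setting, with change = −0.5 × baseline + d × stratum + N(0,1), stratified blocks:

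| Stratum effect d | Baseline-only CI against adjusted CI, 4-9 in smaller stratum | Same, 2-3 in smaller stratum | Baseline-only type I error, 4-9 | Same, 2-3 |
|---|---|---|---|---|
| 0 | 1% narrower | 2-3% narrower | 0.048-0.052 | 0.050-0.053 |
| 0.5 | 1-3% wider | equal to 1% narrower | 0.041-0.048 | 0.044-0.047 |
| 1.0 | 8-12% wider | 2-6% wider | 0.030-0.036 | 0.039-0.047 |

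The adjusted model stays at 0.044-0.058 throughout. At d = 1 with 4-9 in the smaller stratum, the baseline-only model reports a mean SE of 0.52-0.55 against a true SE of 0.49-0.50. The adjusted model's true SE is 0.48-0.50. So the estimator itself barely changes; what is wrong is its stated precision.

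**How much must the stratum explain?** With 9/9 strata, d = 1 corresponds to a share of 0.25/(1 + 0.25) = 0.20 of the variance in change given baseline. At that share a larger simulation (20,000 null trials) gives a CI 12% wider and a type I error of 0.031. At a true treatment effect of 1 SD, power is 0.47 for the baseline-only model and 0.56 for the adjusted one.

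**Dose difference in the nitrite arm only.** Half of such a difference enters the stratum main effect. With 9/9 strata and differences of 0.5 / 1.0 / 2.0 SD, the baseline-only CI is 0.3% narrower / 2% wider / 9% wider. With 15/3 it is 1% narrower / equal / 5% wider.

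**If stratification is not carried out.** Both models hold about 0.05. The baseline-only CI is 4% narrower than the adjusted one at d = 0, 1-3% narrower at 0.5 and 1-8% wider at 1.

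**The case against.** The case for leaving the plan alone is substantial.

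- **Parsimony.** A one-covariate ANCOVA at n = 18 is defensible. With 2-3 subjects in the smaller stratum, adjustment pays only above about 0.5-0.7 SD; with 4-9, above about 0.3 SD. This stands, and is why the point is minor.
- **No evidence of a stratum effect.** The headline figures need age or hypotension risk to predict 4-week change beyond baseline in both arms. A pharmacological dose difference alone does far less. This stands.
- **Already covered.** Section 2.5.3 does mention stratifying by or adjusting for initial dose, so a reader should not infer that the plan ignores it. But nothing commits the team to run or report that analysis.
- **Conservative error in a pilot.** A reader might infer a biased treatment effect or false positives. The documents support neither: the estimate is unbiased and the test rejects too rarely.
- **Planning.** A reader might also infer that the next trial will be oversized. Section 2.5.1 speaks of descriptive statistics, and a stratum term changes no descriptive SD. Its reference to methods close to the proposed analyses could bring in a model variance, but that is an inference, and no section says the next trial will adjust for initial dose. If it does not adjust, the baseline-only variance is the right one. A variance on 15 df also has a 95% interval of 0.55 to 2.40 times the estimate, far wider than the differences at issue.

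**Conclusion.** The point holds in a limited, conditional form. The randomisation and the main Aim 1 models do not match. If stratification is carried out and the stratum predicts change beyond baseline in both arms, the model-based SE and CI are too large and the test is conservative. At an assumed 1 SD effect, the CI excess is about 8-12% with 4-9 of 18 in the smaller stratum and 2-6% with 2-3; up to about 0.5 SD it is negligible. If the stratum acts only through baseline, nothing is lost. If stratification lapses, the SE overstatement disappears.

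The residual variance is too large only by comparison with the within-stratum variance: by 20-28% (4-9) or 11-16% (2-3) at 1 SD. That bears on the next sample size only if that trial is planned from a model variance and adjusts for initial dose.

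This is an optional improvement of low priority. Its main merit is that it settles the choice of model before the data are seen.

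**What to change.** 1. **Section 2.5.3, Aim 1.** For RPE, peak VO₂ and the other outcomes planned for all subjects, replace the sole-covariate wording with: *baseline value of the dependent variable and randomisation stratum (initial dose 20/40 mg, as randomised) as fixed effects.*
2. **Section 2.5.3, Exploratory/Secondary/Sensitivity Analyses.** Commit to reporting the baseline-only model as the sensitivity analysis, and give the residual variance of both models. Keep the descriptive analysis stratified by initial dose, because a stratum main effect cannot show whether the treatment effect differs between dose groups.
3. **Reduced-sample endpoints.** Name the baseline-only model now for iCPET, which is optional (section 2.2, Visit 3B: "Subjects may decline this portion of the testing at consent"), and for MRS, which is restricted in advance (section 2.2, Visit 3A: "Subjects who are identified to have the presence of metal or non-MRI compatible device will not complete Visit 3A (or 6A")). Use no cutoff based on the number analysed.

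The cost is a few sentences and one residual df (15 to 14). If the stratum proves uninformative, the CI widens by about 1% with 4-9 in the smaller stratum, 2-3% with 2-3, and about 4% with a single subject there or without stratification. Outcomes will not all share one main model. No dosing rule changes.
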